#### Rescreening

Patients that fail screening between V1 and V2 may be rescreened for study eligibility only once for the following criteria:

- They do not meet the inclusion criteria for a weekly average NC >1 at V2

- They had an acute illness such as acute sinusitis, nasal infection or upper respiratory infection (E07). These patients can be rescreened only after complete resolution of symptoms
- They took one of the prohibited treatments listed in [Section 8.8.1](#) between V1 and V2.

Patients that are re-screened must sign a new consent form and all of the V1 procedures must be repeated (refer to [Section 8.4](#) for further instructions related to re-screening) unless a prior assessment is performed within the time frame permitted prior to study entry or the V1 baseline CT scan of sinuses and spot urine for biomarker sampling were performed. Patients with positive test for HIV or hepatitis will not be allowed for rescreening.

Note, no waivers will be approved for randomization; all patients must fulfil all eligibility criteria before randomization into the study.

If certain dynamic laboratory tests do not meet the eligibility criteria, these laboratory assessments may be repeated, at the discretion of the investigator, if it is judged to be likely to return to acceptable range for study inclusion within the screening visit window.

For patients who do not fulfil other exclusion criteria, rescreening should be discussed with the Sponsor. In all cases, a given patient can only be re-screened only once.

### **Order of assessments**

During the treatment and post treatment period, if necessary, it is possible to perform the study procedures within a 3 day period as long as these days are within the scheduled visit window and the order of procedures is maintained.

It is recommended that assessments/procedures at a site visit are performed in the following order if applicable:

1. Patient-reported outcomes and other questionnaires:
  - Daily symptoms of NC, loss of smell and anterior and posterior rhinorrhea,
  - SNOT-22,
  - VAS Rhinosinusitis,
  - Reduced sense of taste symptom severity score,
  - QoL (EQ-5D),
  - ACQ-6 (in patients with asthma),
  - Other questionnaires.
2. Procedures.
3. Safety and laboratory assessments.
4. IMP administration.

NIMP boxes should be collected at all visits following provision during all study periods.

IMP boxes should be collected at all visits following provision for home dosing during treatment period.

### 10.1.1 Visit 1 (Week -4/Day -28 ±3 days): Run-in period

Following a discussion of participation in the clinical trial, signed informed consent must be obtained and documented.

The following procedures will then be performed:

- Call IVRS/IWRS to assign patient number, register V1, and obtain first NIMP (NASONEX) box(es).
- Interview to collect patient demographic information, NP information, other medical history (including asthma history, hypersensitivity to aspirin or NSAIDs, NERD, allergy/atopy history, surgical history (including number, type and dates of previous surgery for nasal polyps in the past), and prior and concomitant medications (including background therapy for NP and asthma), courses of SCS in the previous 2 years (number of SCS courses, route of administration doses and duration in the previous 2 years will be entered in the e-CRF), long term antibiotics use [ $>2$  weeks] in the previous year will be also entered in the e-CRF); inform if patient is considered eligible for nasal polyp surgery at study entry.
- Review entry criteria to assess eligibility, with special attention to verify and document the following:
  - Use of SCS for NP within 2 years prior to V1; and/or contraindication/intolerance to SCS; and or prior surgery for NP (whenever in the past),
  - Nasal polyps score of 5 or greater (and at least 2 in each side),
  - Presence of nasal congestion (blockade/obstruction) severity  $\geq 2$  on V1 and loss or reduction of smell and/or rhinorrhea/nasal discharge (anterior/posterior nasal drip),
  - Patients have not received any of the prohibited medications described in [E 03](#) and/or [Section 8.8.1](#).
- Measure vital signs: blood pressure, heart rate, respiration rate, body temperature, weight, height.
- Perform physical examination.
- Perform CT scan (within the time period between V1 and V2, prior to first administration of IMP). In countries for which a specific approval procedure for the CT scan is required by a different committee than the local EC/IRB, patients may be enrolled using a CT available in the previous year or perform an MRI of the sinuses between V1 and V2.
- Perform urine sampling for biomarkers and creatinine.
- Perform spirometry within the time period between V1 and V2, for all patients and ensure that patients with co-morbid asthma have FEV1 $>50\%$ . Spirometry will be performed after the last dose of salbutamol/albuterol or levosalbutamol/levalbuterol has been withheld for at least 6 hours.
- Obtain blood samples for screening clinical laboratory determinations:
  - Hematology (see [Section 9.4.2](#) for details),

- Serum chemistry (see [Section 9.4.2](#) for details).
- Obtain blood samples for hepatitis screen (HBsAg, HBsAb, HBcAb, HCVAb, HIV screen (Anti-HIV-1 and HIV-2 antibodies) and anti-nuclear antibody (ANA). In case of results showing HBsAg (negative), and HBcAb total or HBcAb IgM (positive), an HBV DNA testing may be performed prior to randomization to rule out a false positivity if the Investigator believes the patient is a false positive, or to clarify the serological status if the Investigator finds it unclear to interpret in absence of known HBV infection. In case of results showing HCV Ab (positive), an HCV RNA testing may be performed to rule out a false positivity, if the Investigator believes the patient is a false positive.
  - Note: Anti-ds DNA antibody will be tested if ANA is positive ( $\geq 1:160$  titer).
- Obtain serum  $\beta$ -HCG pregnancy test if WOCBP.
- Perform chest X-ray if no chest imaging (X-ray, CT, MRI) available within the previous year as per local standard of care or if there is local requirement.
  - Note for Japan: According to the request from the health authority, chest X-ray should be performed at V1 if there is no chest imaging (Chest X-ray, CT, MRI) available within 3 months prior to V1 to exclude patients with suspected active or untreated latent tuberculosis.
- Perform nasal endoscopy and send to Central Reader.
- Dispense e-diary/NPIF meter, provide instructions for daily use, and remind patient to bring the device to the next visit.
- NIMP:
  - Dispense MFNS for use as mandatory background therapy throughout the study. Ensure that the patient has sufficient quantity for dosing up until the next visit, knowing that one MFNS bottle contains sufficient doses for either 2 weeks of BID treatment or 4 weeks of QD treatment. Instruct patient on MFNS use and to record daily administration in the e-diary.
- Start AE reporting.
- Review and record all medication use with start date and dose in e-CRF.
  - Check for use of prohibited medications.
- Advise patients with comorbid atopic conditions (such as asthma) not to adjust their treatment without consultation with their physicians.
- Schedule appointment for the next visit.

#### 10.1.2 Visit 2 (Week 0): Randomization

- PRO patient administration in the e-diary: Daily symptoms of NC, loss of smell and anterior and posterior rhinorrhea.
- Inquire about AEs/SAEs and background therapy tolerability.
- Review and record all medication use with start date and dose in e-CRF.
  - Check for use of prohibited medications.
- Download e-diary/NPIF meter and check compliance with use of the mandatory background therapy (MFNS), as defined as:

- $\geq 80\%$  of total number of prescribed “stable dose” sprays taken during the run-in period. Compliance is verified based on MFNS use recorded in the patient e-diary.
- Remind patient to bring the device to the next visit.
- Confirm patient eligibility:
  - Review V1 nasal endoscopy results from central reader to confirm that patient has a score 5 or more and at least 2 each side.
  - Perform and review local endoscopy to confirm that patient has still a score 5 or more and at least 2 each side and record result in e-CRF. If the patient does not have the required scores at the V2 nasal endoscopy, the inclusion criteria are not fulfilled and the patient should not be randomized.
  - Record symptoms of sinusitis, and check the severity average of the last 7 days before visit 2 is  $>1$  for the symptoms: nasal congestion/obstruction.
  - Record spirometry result from V1 and record FEV1 (liters and predicted), FVC and FEF 25-75 result in the e-CRF. Confirm eligibility for patients with FEV1  $>50\%$ .
  - Check patient compliance with daily diary.
- Investigator to assess eligibility for nasal polyp surgery.
- Perform ECG (refer to [Section 9.4.6](#)).
- Obtain urine  $\beta$ -HCG pregnancy test if WOCBP. In case of positive test a serum pregnancy test to confirm the pregnancy should be performed as soon as possible. Pregnancy will lead to definitive screen failure.
- Measure vital signs (blood pressure, heart rate, respiration rate, body temperature, weight).
- Review all Inclusion/Exclusion Criteria to reconfirm eligibility.
  - Reminder that patients receiving prohibited medications described in [Section 8.8.1](#), including rescue with intranasal corticosteroid drops, SCS, or surgery for NP during the run-in period, are NOT eligible for randomization.

**If entry criteria are not met, call IVRS/IWRS to register the visit and screen-fail the patient. Refer to [Section 8.4](#) for details regarding re-screening.**

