Blood biomarkers (TARC, eotaxin-3, periostin, serum total IgE)		X							X				X	
Spot urine for biomarker sampling (LTE4 and PGDM and creatinine)	X	X						X	X				X	
██████████ ██████████		X						X	X					
████████████████████████████████████████		X							X					
██████████ ██████████		X												
██████ ████████		X							X				X	
████████████████████████████████████████		X												

- a The run-in period is 28 days in duration to run in any patient on MFNS, and to collect baseline data. Patients receiving rescue medication with SCS or and surgery during this period will not be randomized. V2 will take place 28 days+/-3 days window after V1. Window for subsequent visits is also +/-3 days. Assessments/procedures at a site visit are performed in the following order if applicable: Patient-reported outcomes and other questionnaires; Procedures; Safety and laboratory assessments; IMP administration.
- b Optional interim visits may be scheduled at site for IMP/NIMP supply or IMP administration.
- c Patients who discontinue treatment early will be assessed as soon as possible using the procedures normally planned for the EOT Visit and will be instructed to return to the study site as described in [Section 10.3.1](#).
- d Past medical history including allergic comorbidities (asthma, aspirin sensitivity, allergic rhinitis etc.). Surgeries for NP will be assessed including number, type and dates of sino-nasal surgeries, polypectomies in the past. Systemic corticosteroids (SCS) use (number of courses, doses, way of administration and duration) in the past 2 years before V1 and/or contraindication/intolerance to SCS, as well as long term antibiotics use (>2weeks) in the previous year will be entered in the e-CRF. NERD: NSAID (non-steroid anti-inflammatory drug) Exacerbated Respiratory Disease will be assessed through a specific questionnaire [Appendix F](#).

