- j* Nasal endoscopy: endoscopy (including use of decongestants before the procedure) will be performed after all other efficacy assessments have been completed for each visit; Standard video sequences will be downloaded by the Investigator to the central reader's secured internet site. For eligibility, central reading of V1 will be used. At V2, Investigator will review V1 results from central reader to confirm entry criteria and reconfirm eligibility based on review of Inclusion/Exclusion Criteria and the V2 endoscopy local reading. To confirm eligibility at V2, only the V1 central reading will be made available to the site. In addition at V2 the investigator will perform the NE to confirm eligibility score and enter the result in the e-CRF. Thus the patient is considered eligible based on a V1 central reading followed by a V2 local reading NPS score of 5 or more and at least 2 each side. The final results of central reading from V2 onward will be made available to the site after the study.
- k* A CT scan should be performed anytime during the run-in period before the first administration of IMP and at V8 (Week 24). Central reading will be used for comparison baseline (BL) to Week 24 for the primary analysis and at EOT. A Week 52 CT scan may be performed if approved by local ethics committees. A Week 52 CT scan may be performed if approved by local ethics committees. Whenever possible a cone beam CT scan should can be utilized. In countries where local EC do not approve a CT scan or for which a specific approval procedure for the CT scan is required by a different committee than the local EC/IRB, patients may be enrolled using a CT available in the previous year or perform an MRI of the sinuses between V1 and V2. These countries will be exempted from all the planned study CT scans until approval from these committees is received. The MRI will be used only for confirmation of exclusion criteria.
- l* During the study the PROs should be completed by the patient in the e-diary, in the following order: daily symptoms of NC, loss of smell and anterior and posterior rhinorrhea; SNOT-22; VAS rhinosinusitis; EQ-5D; ACQ-6 (in patients with asthma).
- m* Health care resource utilization to be collected through the eCRF.

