**Table 1 - Endoscopic nasal polyp score**

Polyp Score	Polyp Size
0	No polyps
1	Small polyps in the middle meatus not reaching below the inferior border of the middle turbinate
2	Polyps reaching below the lower border of the middle turbinate
3	Large polyps reaching the lower border of the inferior turbinate or polyps medial to the middle turbinate
4	Large polyps causing complete obstruction of the inferior nasal cavity

Nasal endoscopy should be performed at the end of the scheduled visits before the administration of IMP and preceded by local administration of anesthetic drugs in combination with a decongestant.

Standard video sequences will be downloaded or sent to centralized reader. Centralized imaging data assessments and scoring by independent physician reviewer(s) for the imaging data will be performed for all endoscopies. To confirm eligibility at V2, only the V1 central reading will be made available to the site. In addition at V2 the investigator will perform the NE to confirm eligibility score and enter the result in the e-CRF. Thus the patient is considered eligible based on a V1 central reading followed by a V2 local reading NPS score of 5 or more and at least 2 each side. The final results of central reading from Visit 2 onward will be made available after the study.

For the analysis of primary endpoint, central reading of V2 will be used for comparison with Week 24 reading. The sites will remove patient-identifying information from the imaging data header prior to sending the imaging data to the central reader.

Further details on nasal endoscopy will be available in a separate operational manual provided to the sites.

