### 10.1 VISIT SCHEDULE

This section describes how the visits are carried out, in chronological order (according to the flow chart [Section 1.2](#) and identical to the order shown in the e-CRF):

The clinical trial consists of three periods, using an add-on therapy approach to INCS:

- Run-in Period (28 days+/- 3 days; V1).
- Randomized treatment period (up to 52 weeks +/- 3 days; Visits 2-10).
- Post-treatment Period (12 weeks; +/- 3 days V11).

The study visits occur on the planned dates (relative to the first injection), as scheduled. The visit schedule should be adhered to within the  $\pm 3$  day visit window.

If a patient is prematurely discontinued from treatment, every attempt should be made for the patient to return to the study site as soon as possible after last IMP administration to perform all assessments planned at the EOT visit and patients will be asked and encouraged to return to the study site for the visit scheduled as described in [Section 10.3.1](#) (early discontinuation) for a 12-week follow up.

Prior to all screening assessments, after discussion of participation in the study, the written consent form [REDACTED] must be signed and dated (see [Section 12.2](#)). At selected sites, requirements for collection of samples for a nasal biomarkers substudy will be included in a separate written informed consent.

Although the screening assessments for this study are grouped under the heading of a single visit in this protocol, it is possible for them to be performed over more than 1 site visit if necessary, as long as the run-in period window prior to Day 1 (V2) is respected. These patients do not need to sign a new consent form and be allocated a new patient number within this same window.

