**If the patient meets all inclusion and does not meet any exclusion criteria:**

- Call IVRS/IWRS to register visit to randomize the patient and receive the first IMP kit number assignment and NIMP (NASONEX) boxes if needed.
- Administer SNOT-22, VAS (for rhinosinusitis), reduced sense of taste severity, QoL (EQ-5D), and ACQ-6 (for patients with asthma).
- Health care resource utilization via e-CRF.
- Administer smell test (UPSIT).
- Obtain blood samples (prior to IMP) for:
  - Hematology laboratories (see [Section 9.4.2](#) for details),
    - Note: Anti-ds DNA antibody will be tested if ANA is positive ( $\geq 1:160$  titer).
  - Serum dupilumab concentration, and anti-drug antibodies,

- Hepatitis B viral load for patients in Japan (or other countries/regions if there is local regulatory requirement) who are HBsAg negative and HBsAb positive at V1,
- Tuberculosis test if required by local regulation,
- Stored DNA sampling, stored serum, and stored whole blood RNA, for those patients who have signed a specific informed consent form.
- Perform urine sampling for biomarkers and creatinine.
- Obtain serum and plasma for biomarkers, see [Section 9.5.2](#).
- [REDACTED]
- [REDACTED]
- Perform blood sampling for total IgE.
- Remind patient to bring the e-diary/NPIF meter to the next visit.
- Reminder: sexually active female patients of reproductive potential are required to practice an acceptable contraception (as defined in [E 15](#) or local protocol amendment in case of specific local requirement) during the entire study duration, while taking dupilumab and for 12 weeks after the last IMP dose. Sexually active male patients should be reminded that if their partner is a woman of childbearing potential, their partner should consider protection by acceptable method(s) of birth control.
- Administer IMP:
  - Patients are monitored for at least 30 minutes (or minimum time required by your local regulator) after the end of administration of IMP for any signs or symptoms of a hypersensitivity reaction,

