2.1.3 Efficacy endpoints

Baseline for efficacy endpoints is defined as the last non-missing value up to randomization but prior to the administration of the first IMP unless otherwise specified.

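### Visit 2 puts the prepared endoscopy and the randomization call before the baseline UPSIT and questionnaires, against the protocol's own rule that endoscopy comes last

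*Protocol*

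**What the plan says.** **The Visit 2 list (Protocol 10.1.2).** After the daily e-diary symptoms, the eligibility step instructs the site to "Perform and review local endoscopy to confirm that patient has still a score 5 or more and at least 2 each side". A patient who falls short is not to be randomized. The remaining steps apply only once all entry criteria are met. The first is the IVRS/IWRS call that randomizes the patient. SNOT-22, VAS, taste severity, EQ-5D and ACQ-6 follow, then UPSIT, samples and the first injection.

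**The ordering rules.** Flow chart footnote j states that "endoscopy (including use of decongestants before the procedure) will be performed after all other efficacy assessments have been completed for each visit". Section 9.1, in the text under Table 1, says "Nasal endoscopy should be performed at the end of the scheduled visits before the administration of IMP", and that it is "preceded by local administration of anesthetic drugs in combination with a decongestant". Footnote a states: "Assessments/procedures at a site visit are performed in the following order if applicable: Patient-reported outcomes and other questionnaires; Procedures; Safety and laboratory assessments; IMP administration". Section 10.1 repeats that last order, but as a recommendation. None of these passages makes an exception for Visit 2.

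**The SAP baseline.** SAP 2.1.3 defines the efficacy baseline, unless otherwise specified, as the "last non-missing value up to randomization but prior to the administration of the first IMP".

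**The concern.** Footnote j and the Visit 2 list cannot both be obeyed. The baseline smell test and questionnaires wait on an eligibility decision that needs the endoscopy score, while footnote j has the endoscopy wait until they are done.

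UPSIT has most at stake. It is a test of smell, and its change from baseline at Week 24 is in the fixed testing sequence of SAP 2.4.4.3. A site that follows 10.1.2 at baseline and footnote j at Week 24 measures one end of the change after anesthetic and decongestant and the other end before them. The count of anosmic patients at baseline (SAP 2.4.4.4.5) rests on the same baseline test.

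A second, separate issue is timing against randomization. In the 10.1.2 order, the Visit 2 values are collected after the call that randomizes the patient, and the flow chart schedules no earlier UPSIT, SNOT-22 or VAS to fall back on.

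**Working it through.** The documents give no figure to reproduce, so the check is a comparison of passages.

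**Step 1. The two orders at Visit 2.**

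| Section 10.1.2 | Footnotes a and j, Section 9.1 |
|---|---|
| Daily symptoms | Daily symptoms, SNOT-22, VAS, taste, EQ-5D, ACQ-6 |
| Local endoscopy (anesthetic, decongestant) | UPSIT |
| Eligibility decision | Local endoscopy (anesthetic, decongestant) |
| Randomization call | Eligibility decision and randomization call |
| SNOT-22, VAS, taste, EQ-5D, ACQ-6 | Safety and laboratory steps |
| UPSIT | First injection |
| Samples, first injection | |

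The rules on the right do not mention the randomization call. It follows the endoscopy there because eligibility needs the score. The conflict with the endoscopy-last rule comes from the position of the endoscopy, not of the call.

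**Step 2. Which baselines are exposed.**

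- NC, TSS and daily loss of smell: averages of diary entries made before randomization. Not exposed.
- NPS: read from the endoscopy itself. Not exposed.
- LMK: a CT scan during the run-in. Not exposed.
- UPSIT: first scheduled at Visit 2, after the endoscopy in the 10.1.2 order. Exposed.
- SNOT-22 and ACQ-6: same position, but the recall periods are two weeks and one week (Protocol 9.2.1.6 and 9.2.2.4), so nasal preparation minutes earlier has less room to act.
- VAS, taste and EQ-5D: same position; none is in the testing hierarchy.

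Within the hierarchy, that leaves UPSIT mainly and SNOT-22 to a lesser degree.

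**Step 3. What it does to the UPSIT change.** Let b be the mean shift in UPSIT caused by the preparation at Visit 2, with no shift at Week 24 because footnote j is followed there.

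- Within an arm: observed mean change = true mean change − b.
- Between arms: (true change on dupilumab − b) − (true change on placebo − b) = true difference.

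The shift cancels if b is the same on average in each arm. That is reasonable, because Visit 2 precedes the first dose and allocation is blinded. The ANCOVA also carries the baseline value as a covariate. If b varies between patients, it adds noise to the baseline and costs some precision. For the anosmia table, a patient is misclassified when the preparation moves the score across the boundary between 18 and 19. The documents give neither the size nor the sign of b.

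**Step 4. The SAP baseline.** The key to SAP Table 4 ends the baseline label 1- at randomization and before the first dose. Label 1+ starts after randomization or the first dose. The Week 2 UPSIT and Week 4 SNOT-22 windows open at 1+. Read by clock time, a Visit 2 value taken after the call is therefore post-baseline. Read by day, it is kept: SAP 2.5.2 and 2.5.4 make the randomization day the efficacy reference day, and Table 4 places Visit 2 for these tests at Day 1. SAP 2.5.4 has a same-day rule for Visit 2 procedures whose time is missing, but states it only for safety and PK/PD variables.

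**The case against.** The best defense is that the Section 10.1 bullets are not a strict sequence. Section 10.1 says "This section describes how the visits are carried out, in chronological order", but this can be read as ordering the visits, and the sentence goes on to refer to the flow chart that carries footnote j. Some lists are plainly not sequential: Visit 1 asks for a check of the polyp score before it lists the endoscopy. Sequencing may also be settled in the separate endoscopy manual, which is not part of these documents.

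This defense succeeds for the later visits. Weeks 16, 24 and 52 (10.1.8, 10.1.10, 10.1.14) list endoscopy before UPSIT, while Week 4 (10.1.4) lists UPSIT first. A reader might infer that UPSIT is compromised at those three visits. The documents do not support that, since nothing there makes UPSIT wait for the endoscopy and footnote j already fixes the order. At Visit 2 the defense fails, because the order is a logical condition and not a matter of layout.

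A reader might also infer a biased treatment difference, on the argument that the sprays act differently at Week 24 in noses with different polyp load. That requires sites to disregard footnote j and a spray effect that differs by arm; the documents give evidence for neither.

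Two further limits stand. Footnote j gives no reason for its order, so the link to the topical agents is an inference from its wording and Section 9.1. Section 8.8.2 describes the agents as allowed before endoscopy, so it is not certain that every patient receives both.

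**Conclusion.** The Visit 2 contradiction is real and should be resolved. If 10.1.2 is followed, it reaches all of the roughly 360 randomized patients at baseline. The consequence is a UPSIT baseline that may be shifted or noisier, and with it the within-arm change and the baseline anosmia count. The effect should balance across arms, given blinded allocation and measurement before the first dose. Its size cannot be stated from the documents. The co-primary endpoints are unaffected, and SNOT-22 and ACQ-6 are less exposed.

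The baseline-timing issue is an ambiguity. A reader might conclude that UPSIT, SNOT-22 and VAS have no valid baseline at all. That goes too far, because the day-level reading of Day 1 keeps the values. They simply do not meet the definition strictly as written.

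**What to change.** Reconcile the passages as follows.

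- In Protocol 10.1.2, move SNOT-22, VAS, taste, EQ-5D, ACQ-6 and UPSIT ahead of both the local endoscopy and the IVRS/IWRS randomization call. This satisfies footnotes a and j and Section 9.1, and it also places the values before randomization as the SAP requires.
- In 10.1.8, 10.1.10 and 10.1.14, list UPSIT before endoscopy, as 10.1.4 already does, so that the lists agree with footnote j.
- In 10.1, state that UPSIT precedes the anesthetic and decongestant given for endoscopy. Limit the sentence to those agents, because wording that covered every topical nasal product would catch the background MFNS and permitted saline lavage.

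The cost is a text change in the protocol and site instructions. Patients who then fail the Visit 2 endoscopy will have completed the questionnaires and one UPSIT (four booklets) unnecessarily.
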